##### Number of Subjects Enrolled by Country and Site ID

This will be based on Enrolled population. The number of subjects summarized by Country, Site ID and Investigator name will be presented. Only the total column will appear.

#### Protocol Deviations

##### Important Protocol Deviations

The number and percentage of subjects who had important protocol deviations defined as part of the protocol deviation management plan for the study, will be summarized. Only the total column will appear.

#### Demographic and Baseline Characteristics

##### Demographic Characteristics

The number and percentage of subjects or summary statistics will be provided for each demographic characteristic and only the total column will appear: Sex, Age (years), Age Group (years), Ethnicity, Race detail, Height, Weight, and Body Mass Index. Age Group (years) will be categorized into three ('≤18', '19-64', '≥65'). Each demographic characteristic will be summarized using the minimum set of summary statistics.

##### Race and Racial Combinations

The five-high level FDA race categories and designated Asian subcategories will be summarized along with all combinations of high level categories which exist in the data. Only the total column will appear.

*Age Ranges*

The number and percentage of subjects within each age range category will be provided. Only the total column will appear. Age range will be categorized into: 18-64 years,  $\geq$ 65-84 years. This is based on the standard of EMA clinical trial results disclosure requirements.

## 7. SAFETY ANALYSES

The safety analyses will be based on the Safety population, unless otherwise specified.

### 7.1. Adverse Events Analyses

Adverse events analyses including the analysis of adverse events (AEs), Serious (SAEs) and other significant AEs will be based on GSK Core Data Standards. The details of the planned displays are provided in [Appendix 9: List of Data Displays](#).

Display Type	Absolute		
	Summary		Individual
	T	F	L
Adverse Events (AEs)			
All AEs by SOC and PT	Y		Y
All AEs by Maximum Intensity	Y		
Drug-Related AEs by SOC and PT	Y		
Drug-Related AEs by Maximum Intensity	Y		
Subject Numbers for Individual AEs			Y
Relationship Between AE SOCs, PT and Verbatim Text			Y
Serious and Other Significant AEs			
Serious AEs			Y
AEs Leading to Withdrawal from Study			Y

**NOTES:**

- T = Table, F = Figures, L = Listings, Y = Yes display generated, SOC = System Organ Class, PT = Preferred Term.
- Summary = Represents TF related to any summaries (i.e. descriptive statistics) of the observed raw data.
- Individual = Represents FL related to any displays of individual subject observed raw data.

#### 7.1.1. Details of Planned Adverse Events Summaries

##### Adverse Events (AEs)

###### All AEs by SOC and PT

The number and percentage of subjects with all relevant adverse events will be summarized by MedDRA System Organ Class and Preferred Term by treatment group. The counting of events and the percentages will be based on the number of subjects on each treatment, so subjects may appear in more than one treatment category.

###### All AEs by Maximum Intensity by SOC and PT

The number and percentage of subjects with adverse events by intensity (e.g., mild, moderate, severe) will be summarized by MedDRA System Organ Class and Preferred Term by treatment group. The counting of events and the percentages will be based on the number of subjects on each treatment, so subjects may appear in more than one treatment category.

Drug-related AEs by SOC and PT

The number and percentage of subjects with all drug-related adverse events will be summarized by MedDRA System Organ Class and Preferred Term. The counting of events and the percentages will be based on the number of subjects on each treatment, so subjects may appear in more than one treatment category.

Drug-related AEs by Maximum Intensity by SOC and PT

The number and percentage of subjects with drug-related adverse events by intensity (e.g., mild, moderate, severe) will be summarized by MedDRA System Organ Class and Preferred Term. The counting of events and the percentages will be based on the number of subjects on each treatment, so subjects may appear in more than one treatment category.

## 7.2. Clinical Laboratory Analyses

Laboratory evaluations including the analyses of Chemistry laboratory tests, Hematology laboratory tests, Urinalysis, and liver function tests will be based on GSK Core Data Standards. The details of the planned displays are in [Appendix 9: List of Data Displays](#).

Display Type	Absolute		
	Summary		Individual
	T	F	L
Chemistry			
Chemistry Changes from Baseline	Y		
Chemistry Values	Y		Y
Chemistry Data Shifts from Baseline Relative to Normal Range	Y		
All Chemistry Data for Subjects with any Value of PCI			Y
Chemistry Values of PCI			Y
Haematology			
Haematology Changes from Baseline	Y		
Haematology Values	Y		Y
Haematology Data Shifts from Baseline Relative to PCI Criteria	Y		
All Haematology Data for Subjects with any Value of PCI			Y
Haematology Values of PCI			Y
Urinalysis			
Urinalysis Concentration Changes from Baseline (Gravity and pH)	Y		
Urinalysis Data (Gravity and pH)	Y		Y
Urinalysis Data (Glucose, Protein, Blood, Ketones, Bilirubin, and Urobilinogen)	Y		Y
Hepatobiliary (Liver)			
Liver Monitoring/Stopping Event Reporting			Y
Medical Conditions for Subjects with Liver Stopping Events			Y

---

**NOTES:**

- T = Table, F = Figures, L = Listings, Y = Yes display generated, SOC = System Organ Class, PT = Preferred Term.
- Summary = Represents TF related to any summaries (i.e. descriptive statistics) of the observed raw data.
- Individual = Represents FL related to any displays of individual subject observed raw data.

### 7.2.1. Details of Planned Clinical Laboratory Displays

#### Chemistry/Haematology Laboratory Tests

##### Laboratory Changes from Baseline and Values

Each quantitative laboratory test and the changes in value from baseline will be summarized at every assessed time point using n, mean, standard deviation, median, minimum, and maximum by treatment group.

##### Laboratory Data Shifts from Baseline Relative to PCI Criteria

The number and percentage of subjects with laboratory results within each PCI criteria category (Low, W/in Range, High) during each planned time assessment will be summarized by treatment group relative to their baseline category by laboratory test, where PCI criteria are available. The percentages are based on the number of subjects in the treatment group with data for the laboratory test at the specified planned time (n). The worst case post-baseline is used to summarize the subjects' overall worst case shifts during the post-baseline period.

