2: Follow-up Visit to occur at least 7 days, and no greater than 14 days after last study treatment administration. If a participant withdrew from the study after received GSK2982772 or placebo dose, the safety assessments listed at follow-up visit will be required.

Detailed Time and Events Table for Days 1-4 (common Period1-4)

Procedure ¹	Day -1	Day 1																									
		Pre-dose	0	20 min	40 min	1 hr	1.5 hr	2 hr	3 hr	4 hr	5 hr	7 hr	7 hr 20 min	7 hr 40 min	8 hr	8.5 hr	9 hr	10 hr	11 hr	12 hr	14 hr	14 hr 20 min	14 hr 40 min	15 hr	15.5 hr		
Admission	X																										
Physical Examination	X	X						X				X ⁶													X ⁶		
Hema/Chem/Urinalysis tests	X																										
Vital signs ²		X						X				X ⁶												X ⁶			
12-lead ECG		X						X				X ⁶											X ⁶				
Cardiac telemetry ³		<=====																									
PK blood sampling		X		X	X	X	X	X	X		X	X ⁷	X	X	X	X	X	X	X		X	X ⁷	X	X	X	X	X
Neurological Examination	X							X																X ⁸			
Study Treatment			X									X											X				
Pharmacogenetic Sampling (PGx) ⁴		<=====																									
Meals Served	X							X ⁹			X ⁹											X ⁹					
AE Review ⁵		<=====																									
Concomitant Medication Review		<=====																									
Discharge																											

Procedure ¹	Day 2								Day 3		Day 4
	16 hr	17 hr	19 hr	22 hr	24 hr	28 hr	32 hr	36 hr	48 hr	60 hr	72 hr
Admission											
Physical Examination					X			X	X		X
Hema/Chem/Urinalysis tests											X
Vital signs ²					X				X		X
12-lead ECG					X				X		X
Cardiac telemetry ³	=====>										
PK blood sampling	X	X	X	X	X	X	X	X	X	X	X
Neurological Examination					X				X		X
Study Treatment											
Pharmacogenetic Sampling (PGx) ⁴	=====>										
Meals Served						X ¹⁰		X ¹⁰	X ¹⁰	X ¹⁰	
AE Review ⁵	=====>										
Concomitant Medication Review	=====>										
Discharge											X

1: In this study, baseline is Day -1 and Day 1 pre-dose tests.

2: Vital signs include PR, BPs and temperature.

3: Only 24 hrs following the first dose administration

4: A PGx blood sample will be collected at any time during the study after randomization and provided informed consent for genetic reserch. The participation is optional for each subject.

5: All SAEs will be collected from the signing of the ICF until the follow-up visit at the time points specified. All AEs will be collected from the start of treatment until the follow-up visit at the time points specified.

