10.4. Statistical Analyses

10.4.1. Safety Analyses

All safety analyses will be performed on the Safety Population. Safety data will be presented in tabular and/or graphical format and summarized descriptively according to GSK's Integrated Data Standards Library (IDSL) standards.

The tables, figures, and listings will use the Safety Population unless otherwise specified. AEs, changes in clinical laboratory values, 12-Lead ECGs, findings during continuous cardiac telemetry and vital signs will be summarized by dose group (i.e. placebo, 60 mg, 120 mg, and 240 mg) to assess the safety and tolerability of GSK2982772. The safety and tolerability results will not to be formally compared between each group and comparison with placebo will be based on review of descriptive summaries.

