### 9.3. Appendix 3: Study Phases and Treatment Emergent Adverse Events

#### 9.3.1. Study Phases

Assessments and events will be classified according to the time of occurrence relative to the date of dosing date.

Study Phase	Definition
Pre-Treatment	Date $\leq$ Previous Day of Dosing Date in Period 1
Period 1	Previous Day of Dosing Date in Period 1 $\leq$ Date $<$ Previous Day of Dosing Date in Period 2
Period 2	Previous Day of Dosing Date in Period 2 $\leq$ Date $<$ Previous Day of Dosing Date in Period 3
Period 3	Previous Day of Dosing Date in Period 3 $\leq$ Date $<$ Previous Day of Dosing Date in Period 4
Period 4	Previous Day of Dosing Date in Period 4 $\leq$ Date

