
 
Unscheduled visits will not be included in summary tables and/or figures.
 
All unscheduled visits will be included in listings.
 
	
Descriptive Summary Statistics	
Continuous Data	Refer to IDSL Statistical Principle 6.06.1
Categorical Data	N, n, frequency, %
Graphical Displays	

 
Refer to IDSL Statistical Principles 7.01 to 7.13.
 
[Insert as Required: If any publication related displays have been specified, please provide relevant details]
 
	

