## 9.5. Appendix 5: Derived and Transformed Data

### 9.5.1. General

Multiple Measurements at One Analysis Time Point	

 
Mean of the measurements will be calculated and used in any derivation of summary statistics but if listed, all data will be presented.
 
Participants having both High and Low values for Normal Ranges at any post-baseline visit for safety parameters will be counted in both the High and Low categories of “Any visit post-baseline” row of related summary tables. This will also be applicable to relevant Potential Clinical Importance summary tables.
 
	
Study Day	

 
Calculated as the number of days from First Dose Date: 
 
Ref Date = Missing → Study Day = Missing
 
Ref Date < First Dose Date → Study Day = Ref Date - First Dose Date
 
Ref Date ≥ First Dose Date → Study Day = Ref Date - (First Dose Date) + 1
 
 
 
	
Period Day	

 
Calculated as the number of days from Dosing Date in each period. For study phase derivation, see Appendix 3. 
 
If Study Phase of Ref Assessment or Event = Pre-Treatment or Missing → Period Day = Missing
 
If Study Phase of Ref Assessment or Event = Period X and Ref Date is on or after Dosing Date in Period X → Period Day = Ref Date - Dosing Date in Period X + 1 day
 
If Study Phase of Ref Assessment or Event = Period X and Ref Date is before Dosing Date in Period X → Period Day = Ref Date - Dosing Date in Period X
 
 
 
 
Note: X takes a value of 1, 2, 3, 4.
	

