### 9.9.5. Safety Tables

Safety: Tables					
No.	Population	IDSL / Example Shell	Title	Programming Notes	Deliverable [Priority]
Adverse Events (AEs)					
2.1.	Safety	AE1CP	Summary of All Adverse Events by System Organ Class and Preferred Term	ICH E3	SAC
2.2.	Safety	AE5A	Summary of All Adverse Events by Maximum Intensity by System Organ Class and Preferred Term	ICH E3	SAC
2.3.	Safety	AE1CP	Summary All Drug-Related Adverse Events by System Organ Class and Preferred Term	ICH E3 .	SAC
2.4.	Safety	AE5A	Summary of All Drug-Related Adverse Events by System Organ Class and Preferred Term and Maximum Intensity	ICH E3 .	SAC
Laboratory: Chemistry					
2.5.	Safety	LB1	Summary of Chemistry Values		SAC
2.6.	Safety	LB1	Summary of Chemistry Changes from Baseline	ICH E3	SAC
2.7.	Safety	LB4	Summary of Chemistry Data Shifts from Baseline Relative to PCI Criteria	ICH E3	SAC
Laboratory: Hematology					
2.8.	Safety	LB1	Summary of Hematology Values		SAC
2.9.	Safety	LB1	Summary of Hematology Changes from Baseline	ICH E3	SAC
2.10.	Safety	LB4	Summary of Hematology Data Shifts from Baseline Relative to PCI Criteria	ICH E3	SAC

CONFIDENTIAL

205037

Safety: Tables					
No.	Population	IDSL / Example Shell	Title	Programming Notes	Deliverable [Priority]
Laboratory: Urinalysis					
2.11.	Safety	LB1	Summary of Urinalysis Data (Gravity and pH)		SAC
2.12.	Safety	LB1	Summary of Urinalysis Concentration Change from Baseline (Gravity and pH)	ICH E3	SAC
2.13.	Safety	UR3b	Summary of Urinalysis Data (Glucose, Protein, Blood, Ketones, Bilirubin, Urobilinogen)		SAC
Neurological Examination					
2.14.	Safety	NE1	Summary of Neurological Examination		SAC
ECG					
2.15.	Safety	EG1	Summary of ECG Findings	IDSL	SAC
2.16.	Safety	EG2	Summary of ECG Values		SAC
2.17.	Safety	EG2	Summary of Change from Baseline in ECG Values by Visit	IDSL	SAC
2.18.	Safety	HM1	Summary of Cardiac Telemetry	IDSL	SAC
2.19.	Safety	HM2	Summary of Cardiac Telemetry Abnornormalities	IDSL	SAC
Vital Signs					
2.20.	Safety	VS1	Summary of Vital Signs	IDSL	SAC
2.21.	Safety	VS1	Summary of Change from Baseline in Vital Signs	ICH E3	SAC

CONFIDENTIAL

205037

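### The worst-case laboratory shift rows have no stated end; read with the open-ended Period 4, they would give 240 mg a longer window than 60 or 120 mg

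*SAP*

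**What the plan says.** SAP 7.2.1 tabulates shifts relative to the limits of potential clinical importance (PCI) by treatment group. It does so at each planned time, with the n for that time, and then adds a pooled row that uses each man's worst value after baseline to show the "overall worst case shifts during the post-baseline period". No end to that period is given. The displays concerned are Table 2.7, "Summary of Chemistry Data Shifts from Baseline Relative to PCI Criteria", and its haematology counterpart, Table 2.10. SAP 9.5.1 describes a similar pooled row, which counts men with high or low values "at any post-baseline visit for safety parameters", again with no window.

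SAP 9.3.1 sorts assessments by date into a pre-treatment phase and Periods 1 to 4. Each of Periods 1 to 3 closes before Day -1 of the next period. Period 4 starts on the "Previous Day of Dosing Date in Period 4" and has no upper limit. There is no follow-up phase. SAP 9.6.1 refers to assessment windows in Appendix 3, but that appendix contains only the study phases.

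The schedule of activities (Protocol section 2) places laboratory panels on Day -1 and at 72 hr (Day 4) of each period, plus one at follow-up: "Follow-up Visit to occur at least 7 days, and no greater than 14 days after last study treatment administration". SAP 5.2 resets baseline in each period. SAP 9.4.2 adds: "Unscheduled visits will not be included in summary tables and/or figures". Follow-up is a scheduled visit, so that rule does not remove it.

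**The concern.** In this ascending design the last period is not balanced over treatments. If the follow-up panel belongs to Period 4, it is credited mostly to the top dose, partly to placebo and never to the two lower doses. A worst-case row gives every extra panel another opportunity to show a shift. The 240 mg column could then look somewhat worse than 60 mg, 120 mg or placebo purely because its window is longer.

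Change in laboratory values is a named safety endpoint. Protocol 10.4.1 plans no formal comparison between groups and says that "comparison with placebo will be based on review of descriptive summaries". The tables themselves are therefore the comparison, and 240 mg TID is the highest dose intended for Phase 2b.

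**Working it through.** **Inputs.** Four sequences of 3 men (Protocol 5.1 and 10.1); panel times from Protocol section 2; phase limits from SAP 9.3.1. The count assumes 12 completers and no missing panel.

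**The plan's own figure.** Protocol 10.1 states 12 men on each treatment. Every sequence contains every treatment once, so 4 x 3 = 12, as stated.

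**Who carries the follow-up panel.** The Period 4 treatment is 240 mg in sequences A, B and C (9 men) and placebo in sequence D (3 men). It is never 60 or 120 mg.

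**Post-baseline panels per column.** Each period contributes one panel (72 hr) per man, because the Day -1 panel of the next period belongs to that next period. Period 4 adds follow-up.

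| Treatment | 72 hr panels | Follow-up panels (m) | Total |
|---|---|---|---|
| 60 mg | 12 | 0 | 12 |
| 120 mg | 12 | 0 | 12 |
| 240 mg | 12 | 9 | 21 |
| Placebo | 12 | 3 | 15 |

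Check: 12 + 12 + 21 + 15 = 60 = 12 men x (4 + 1) panels.

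**Size with no drug effect.** Let p be the chance that a panel shows a shift on a given test, the same for every treatment, and let rho be the correlation between a man's two panels. The documents give neither, so both are assumptions. The chance of a shift in at least one of two panels is p + p(1-p)(1-rho). Expected men in the worst-case row, per test, are

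12p + m x p(1-p)(1-rho).

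With rho = 0:

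| p | 60 and 120 mg | Placebo | 240 mg |
|---|---|---|---|
| 1% | 0.12 (1.0%) | 0.15 (1.25%) | 0.21 (1.74%) |
| 5% | 0.60 (5.0%) | 0.74 (6.2%) | 1.03 (8.6%) |

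The excess of 240 mg over 60 mg is 9p(1-p)(1-rho):

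- p = 1%: 9 x 0.01 x 0.99 = 0.09 man at rho = 0, and 0.04 at rho = 0.5.
- p = 5%: 9 x 0.05 x 0.95 = 0.43 man at rho = 0, and 0.21 at rho = 0.5.
- rho = 1: no excess at any p.

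**Under the proposed rule.** Limiting the pooled row to the 72 hr panel gives 12, 12, 12 and 12.

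**The case against.** The strongest objection is that SAP 7.2.1 never mentions follow-up. Its entry into the row comes from joining 7.2.1 to the general phase table in 9.3.1. Tables 2.7 and 2.10 use the standard shell LB4, and SAP Appendix 10 shows mock shells only for the two PK model tables. A reader might infer that the programmed tables will include the follow-up panel. The documents do not establish that. They leave the window open, and their stated rules, followed literally, lead there. This stands, and the conclusion is conditional for that reason. No text excludes follow-up either.

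The like-for-like comparison is also already planned. Shifts, values and changes are tabulated at each time point, so Day 4 can be compared with Day 4, and a follow-up row would show its own n. Listings 21 to 26 give all chemistry and haematology data and the values outside PCI limits. This stands too, and confines the point to one pooled row in two tables, plus any any-visit row.

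The PCI limits are wide. ALT is flagged from 2 x ULN in men who could not enter above 1.5 x ULN, and sodium only below 130 or above 150 mmol/L. The low end of the range for p is the more plausible.

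Finally, crediting late findings to the last treatment matches the open-ended Period 4 rule for adverse events (SAP 9.3.1.1), and it hides no 240 mg event. As a convention for listing data that is reasonable. It does not make a pooled row comparable across columns with different windows.

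**Conclusion.** The point holds as a minor gap in specification. Read together, SAP 7.2.1 and 9.3.1 would give the 240 mg column a longer worst-case window in 9 of 12 completers and placebo in 3 of 12, with none at 60 or 120 mg. Those counts are exact for 12 completers. A man who withdraws also has follow-up assessments, and his panel would fall under his last treatment, so dropouts would change the counts. The excess per test is a fraction of a man and depends on assumed values of p and rho.

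A reader might go further and infer that the laboratory safety comparison as a whole is biased against 240 mg, or that dose escalation could be misled. The documents support neither. Per-time rows and listings are unaffected. Escalation under Protocol 5.4 and 8.1.1 rests on blinded review of each completed dose level, and does not use this row.

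**What to change.** Add to SAP 7.2.1, before unblinding: the worst-case and any-visit post-baseline rows use only the Day 4 (72 hr) panel of each period; the follow-up panel is shown as a separate row, with its own n, under the last treatment received.

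This is one sentence for two tables. It uses data already collected and leaves baseline definitions, listings and study conduct unchanged. The cost is that, with unscheduled visits kept out of tables, the worst-case row then equals the Day 4 row and may be dropped. A footnote saying that follow-up is counted under the Period 4 treatment would be lighter still, but it would only disclose the unequal windows and not remove them.

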#### Urinalysis Laboratory Tests

##### Urinalysis Concentration Changes from Baseline (Gravity and pH)

Gravity and pH test and the changes in value from baseline will be summarized at every assessed time point using n, mean, standard deviation, median, minimum, and maximum by treatment group.

##### Urinalysis Data (Glucose, Protein, Blood, Ketones, Bilirubin, and Urobilinogen)

The number and percentage of subjects with the above urinalysis results (character results) will be summarized by treatment group.

### 7.3. Other Safety Analyses

The analyses of non-laboratory safety test results including ECGs and vital signs will be based on GSK Core Data Standards, unless otherwise specified. The details of the planned displays are presented in [Appendix 9: List of Data Displays](#).

Display Type	Absolute			Change from BL		
	Summary		Individual	Summary		Individual
	T	F	L	T	F	L
Neurological Examination						
Neurological Examination Findings	Y		Y			
ECG						
ECG Findings	Y		Y			
ECG Values	Y		Y	Y		
All ECG Values for Subjects with any Value of PCI			Y			
Cardiac Telemetry	Y					
Cardiac Telemetry Abnormalities	Y					
Clinically Significant Cardiac Telemetry Abnormalities			Y			
Vital Signs						
Vitals Values	Y		Y	Y		
All Vital Signs for Subjects with any Value of PCI			Y			

**NOTES:**

- T = Table, F = Figures, L = Listings, Y = Yes display generated, PCI = Potential Clinical Importance
- Summary = Represents TFL related to any summaries (i.e. descriptive statistics) of the observed raw data.
- Individual = Represents FL related to any displays of individual subject observed raw data.

#### 7.3.1. Details of Planned Other Safety Displays

##### ECG

###### ECG Findings

The number and percentage of subjects with ECG findings (ECG interpretation) will be summarized by treatment group..

###### ECG Values

Each ECG parameter value and the change from baseline will be summarized by treatment group at every assessed time point using n, mean, standard deviation, median, minimum, and maximum.

